8.1 Study hypotheses

This study is a pilot study to estimate the differences in the incidences in adverse treatment outcomes and excess toxicity. Consequently, the focus will be in describing event rates in each study arm and estimating the differences in event rates using odds-ratio's together with 95% confidence intervals (CIs) and not on formal hypothesis testing. P-values for comparisons of event rates (adverse treatment outcomes and safety endpoints) between intervention and control arms will be provided, but will need to be interpreted with care.

8.2 Variables of interest

All variables of interests are event rates as defined in Section 3.1. In each analysis, if a patient has two events for the analysis of interest (e.g. relapse followed by death), the first endpoint will be taken into account.

8.3 Statistical methods

8.3.1 Analysis populations

We will analyse the efficacy data both using Intention-to-Treat and Per-Protocol approaches, with Intention-to-Treat as primary approach. In the Intention-to-Treat analysis, all patients will be analysed according to their randomized allocation, even in case they receive another treatment regimen, show protocol violations prior to or during the study, or are lost-to follow. Patients lost-to-follow-up before the 12 month post treatment follow-up or who do not provide a sputum smear are considered to be failures in this analysis, unless they are known to have moved out of the study region. In the per-protocol analysis only patients who receive study drug as planned, have complete follow-up (till 2.5 years or development of a study endpoint) or have reached a study endpoint at an earlier time-point, and follow the protocol as planned are included.

Safety analysis will be performed using an all-patients-treated approach, including all patients who received at least a single dose, and according to the treatment regimen actually received.

8.3.2 Baseline characteristics

Patients in each treatment group, and in each hospital, will be described with respect to baseline characteristics. The clinical importance of any imbalance will be noted though statistical tests of significance will not be undertaken.

8.3.3 Primary analysis

Counts and proportions (end 95% CI) of patients with any adverse treatment outcome, and by adverse treatment outcome category, will be presented. The confidence intervals for incidences will be estimated using Wilson's score method. Odds ratio's (ORs) and 95% CIs for the OR will be estimated from a logistic regression model with effects for arm (intervention vs control), hospital, and stratum (new/re-treatment case). The p-value for the test of no difference among arms will be presented. If the number of events is low a logistic regression model with an effect for hospital may be used instead of the full model proposed.

Similar analysis will be performed for the primary safety endpoint.

8.3.4 Secondary and tertiary analysis

Secondary Objectives

1. *To assess whether the study regimen also cures low-level rifampicin resistant TB*

Adverse treatment outcomes will be described and compared among treatment groups in subgroups defined by initial rifampicin resistance mutations (performed in all patients) detected:

- none

- low-level
- high

2. *To assess the effectiveness of standard auramine versus FDA vital staining screening at two weeks of treatment for early switch of non-responding rifampicin resistant TB to MDR-TB treatment*

The proportion of initial rifampicin resistant case detected by FDA (i.e. the sensitivity of FDA) will be estimated together with 95% CI. The same analysis will be performed for auramine or ZN AFB smears and compared with FDA. Also the number of referrals needed with both techniques will be compared.

3. *To assess the negative predictive value of conversion at 2 weeks for relapse*

The Negative Predictive value (and 95% CI) of conversion in the intervention arm will be estimated as the % of relapses among those with a minimum 1 log decline in the number of AFB, or who are already negative or only scanty positive on AFB smear (auramine or FDA) at week 2.

4. *To estimate the proportion of acquired rifampicin resistance among failures and relapses*

Proportions will be estimated together with 95% confidence intervals, using the number of failure / relapse cases without mutation detected at diagnosis as the denominator and comparing intervention and control arms.

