i.e. pyrazinamide, or very low kill, i.e. ethambutol). We have limited data from a study using standard auramine as well as FDA vital staining on serial sputa over the first 2 weeks, showing that in susceptible cases the AFB counts usually decrease by 1 log after 1 week, and by 2 logs after 2 weeks. However, there were exceptions, and the quantification of AFB in direct smears is not that reproducible, so that the exact cut-off or algorithm to screen patients for DST referral needs to be better defined. The challenge will be to balance good sensitivity of screening for serious initial drug resistance and/or extensive disease, versus excessive numbers of patients to be referred for in-depth investigations. To apply earlier screening for drug resistance also to the control group, absence of fever resolution at two weeks (as lead symptom of unsatisfactory clinical improvement) will be used as an alternative referral criterion for rapid DST. This would be the simplest possible screening tool, and may even be more appropriate considering the highly unsatisfactory results of treatment follow-up by means of microscopy in many TB control programmes.

The WHO recommended Xpert MTB/RIF assay as well as lineprobe assays for molecular detection of resistance cover a large variety of mutations in the responsible genes by incorporation of probes covering the relevant stretch of wildtype DNA, plus- in the case of the lineprobe assay- a few 'mutant' probes that confirm the most frequent mutations. A positive signal from the mutant probes will always correctly indicate that this mutation is present. For the wildtype probes a negative signal (absent or low-intensity bands; delayed amplification) is interpreted as resistance. However, this is not satisfactory since poor reactions occur regularly with poor specimens or technique, and a false negative signal (falsely indicating resistance) is possible with "silent mutations", i.e. a change in nucleotide that still codes for the same amino-acid.

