3. STUDY OBJECTIVES

Primary objective:

To compare a high-dose rifampicin standard TB regimen of 6 months duration with standard TB regimen with respect to adverse treatment outcome (relapse, failure, death and default) and toxicity, in TB cases (new or retreatment, pooled) not shown to have initial rifampicin resistance before one of the standard treatment outcomes applies.

Secondary objectives:

1. To assess whether the study regimen also cures low-level rifampicin resistant TB: by comparing and describing adverse treatment outcomes by initial rifampicin mutations (none, low-level, high)
2. To assess the effectiveness of FDA vital staining screening at two weeks of treatment for early switch of non-responding rifampicin resistant TB to MDR-TB treatment, versus clinical evaluation based on fever resolution. The proportions of rifampicin resistant cases started on MDR treatment within the first 2 months of primo-treatment as well as the proportion of initially present resistance never switched to the MDR regimen and not cured will be compared between the two arms.
3. To assess the negative predictive value of conversion at 2 weeks for relapse
4. To estimate the proportion of acquired rifampicin resistance among failures and relapses
5. To compare the predictive value of auramine with FDA staining at 2 weeks to predict unfavourable outcomes

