5.4 Laboratory procedures

All analysis of clinical trial samples will be carried out in compliance with Good Clinical Laboratory Practice (GCLP). A Lab Analytical Plan will be available, in line with WHO-GCLP

FDA vital staining at 1 and 2 weeks will be used as part of the screening to identify intervention arm patients to be referred for rapid DST, and promptly switched to the MDR regimen if rifampicin resistant. Also an auramine AFB smear will be performed for comparison with FDA screening. Further follow-up will be standard and the same in the study and control cohort, by auramine AFB-smear at 2/3 months, 5 months and at end of treatment, when patients may again be referred for DST. Patients found positive on smear will be declared failure as per NTP definitions and registered for retreatment. Also relapse will be declared based on smears, as per NTP definitions. All failure and relapse cases will have sputum referred for conventional culture and DST, besides the rapid screening for rifampicin resistance. If not found resistant to this drug, such recurrence patients belonging to the intervention arm will not be re-started on the standard Cat. 2 but on the study regimen.

The initial, ethanol preserved pre-treatment specimen from all enrolled cases will be forwarded to ITM, Antwerp, for DNA sequencing of the *rpoB* gene. The *katG* and *inhA* genes will only be sequenced if an *rpoB* mutation is detected. All strains from cases diagnosed with rifampicin resistance at any time (2 weeks; failure; relapse or default), and all failure or relapse recurrence strains will also be forwarded to ITM, Antwerp. ITM will perform full DST and species identification, besides DNA sequencing of the *rpoB* genes. This will allow to compare the distribution of resistance-conferring mutations in the two study arms, and to identify possible acquired rifampicin resistance comparing

with the pre-treatment sequence. Spoligotyping on both pre-treatment sputum and recurrence isolate will be performed for confirmation of strain identity of all recurrences, to avoid confusion with re-infection, and to confirm presumed acquired resistance.

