## **7. Analysis of secondary objectives**

7.1. To assess whether the study regimen also cures low-level rifampicin resistant TB

The interaction between treatment differences and initial rifampicin resistance mutations detected will be tested in the logistic regression model from the main analysis. Initial rifampicin resistance mutations detected is categorized as:

- None
- Low-level
- High

7.2. To assess the effectiveness of FDA vital staining screening at two weeks of treatment for early switch of non-responding rifampicin resistant TB to MDR-TB treatment, versus clinical evaluation based on fever

The proportions of initial rifampicin resistant cases started on MDR treatment within the first 2 months of primo-treatment as well as the proportion of initially present resistance never switched to the MDR regimen and not cured will be compared between the two arms using the chi-squared or Fisher's exact test.

7.3. To assess the negative predictive value of conversion at 2 weeks for relapse

The complement of the Negative Predictive value (with 95% Wilson CI) of conversion in the intervention arm will be estimated as the % of relapses among those who are already completely negative on AFB smear (auramine or FDA) at week 2.

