7.4. To estimate the proportion of acquired rifampicin resistance among failures and relapses

Proportions per treatment arm will be estimated together with 95% Wilson confidence intervals, using the number of failure / relapse cases without mutation detected at diagnosis as the denominator.

7.5. To compare the predictive value of auramine with FDA staining at 2 weeks to predict unfavourable outcomes

The ROC curves of auramine resp. FDA staining at 2 weeks to predict adverse treatment outcome will be plotted and compared using the nonparametric approach of DeLong, DeLong, and Clarke-Pearson (1988). In addition, the proportion of referrals to rapid DST will be compared between auramine and FDA using the chi-squared or Fisher exact test.

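### The protocol defines objective 2 in two ways, and the SAP's final analysis omits the planned sensitivity of week-2 FDA and auramine for initial rifampicin resistance

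*Protocol*

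**What the plan says.** **Protocol, synopsis and section 3.** Objective 2 compares FDA screening at two weeks with clinical judgement based on fever. Section 3 adds two measures, both compared between arms. One is how many resistant patients begin the MDR regimen in the first two months; the other is how many with resistance at the start were neither switched nor cured.

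**Protocol 8.3.4.** Under the same objective number, the heading becomes auramine versus FDA and the analysis has three parts:
- Sensitivity of FDA: "The proportion of initial rifampicin resistant case detected by FDA (i.e. the sensitivity of FDA) will be estimated together with 95% CI"
- Sensitivity of conventional smears: a matching estimate for auramine or ZN, set against the FDA figure.
- Referral load: the count of patients that each stain would send for rapid DST, also compared.

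**SAP 7.2.** The final analysis of objective 2 uses the section 3 measures, starting with "The proportions of initial rifampicin resistant cases started on MDR treatment within the first 2 months of primo-treatment", and tests them between arms by chi-squared or Fisher's exact test.

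**SAP 7.5.** For objective 5, ROC curves of the two stains "to predict adverse treatment outcome will be plotted and compared". The proportions referred for rapid DST are also compared between stains, by chi-squared or Fisher's exact test.

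**SAP 5.** The interim analysis of the first 500 patients compares the percentage of resistance missed between arms. SAP 1 says that genetic resistance results will by then exist for only part of these patients.

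**Protocol 5.4.** The reference standard is collected for everyone: "The initial, ethanol preserved pre-treatment specimen from all enrolled cases will be forwarded to ITM" for rpoB sequencing.

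**The concern.** This is a pilot, and protocol 2.1 says its results will help adapt the resistance-screening algorithm for a larger study. Protocol 1.2 concedes that "the exact cut-off or algorithm to screen patients for DST referral needs to be better defined". For that purpose one wants to know what share of initially resistant patients each stain flags at week 2. Protocol 8.3.4 plans that figure, and baseline sequencing of all enrolled patients supplies a reference that does not depend on who was referred. Verification bias should therefore be small. If the SAP is followed as written, the final report will show how many resistant patients were switched and how the stains relate to later outcome. It will not show how often each stain picked up resistance that was present at the start.

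**Working it through.** **1. Does any SAP section give the 8.3.4 sensitivity in the final analysis?**

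| SAP section | Quantity | Why it is not the 8.3.4 sensitivity |
|---|---|---|
| 7.2 | Switched within 2 months; never switched and not cured, by arm | Also depends on referral, the DST result, the month-2 smear and the switch itself. It cannot assess auramine, because the week-2 decision rests on FDA. |
| 7.5, ROC curves | Each stain against adverse treatment outcome | The target is outcome, not initial resistance. SAP 4.2 removes patients found resistant and switched before an outcome, so many of the screen's true positives leave the data. |
| 7.5, referrals | Proportion referred, by stain | Keeps the referral part of 8.3.4. Contains no resistance status. |
| 5 (interim) | Percentage of resistance missed, by arm | This is the complement of sensitivity, but only in the first 500 patients, with partial genetic data, no confidence interval and no auramine figure. |

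Of the three parts of 8.3.4, the referral comparison survives and the two sensitivities do not. The interim data also span a period when staining was still being improved, which is why SAP 5 stratifies the intervention arm by 2014 versus 2015.

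**2. Expected number of resistant patients.** Protocol 8.4 expects about 20 in total, 10 per arm, from 2010 data. Protocol 1.1 gives 2% MDR-TB among new cases in 2010. Applying 2% to all 1000 patients gives 1000 × 0.02 = 20, or 10 per arm, so the plan's figure reproduces.

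**3. Precision of a restored sensitivity.** The Wilson interval, which the SAP uses for other proportions, is [p + z²/2n ± z√(p(1−p)/n + z²/4n²)] / (1 + z²/n) with z = 1.96.

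For an assumed 8 of 10:
- centre: (0.8 + 0.192)/1.384 = 0.717
- half-width: 1.96 × √(0.016 + 0.0096)/1.384 = 0.227
- interval: 49.0% to 94.3%

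The observed counts are assumptions, shown as a range:

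| Detected | Sensitivity | Wilson 95% CI |
|---|---|---|
| 5/10 | 50% | 23.7% to 76.3% |
| 8/10 | 80% | 49.0% to 94.3% |
| 9/10 | 90% | 59.6% to 98.2% |
| 10/10 | 100% | 72.2% to 100% |

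At the interim, about 250 intervention patients × 0.02 = 5 resistant cases at most, given partial genetic data. An assumed 4/5 then gives 37.6% to 96.4%.

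**4. Precision of the comparison that SAP 7.2 keeps.** With 10 against 10 resistant patients, Fisher's exact test needs a gap of 5 to 6 patients to reach 5%: 5/10 against 10/10 gives p = 0.033, and 2/10 against 8/10 gives p = 0.023.

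**5. Structure of the stain comparison.** Both stains are read at week 2 in the same intervention patients. The two referral proportions in SAP 7.5 are therefore paired, and a chi-squared or Fisher test for independent groups does not fit them.

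**The case against.** The strongest reply is that the SAP delivers objective 2 as the protocol states it. The synopsis and section 3 both set FDA against fever, and SAP 7.2 reproduces the section 3 measures. The heading in 8.3.4 is the outlier. The dependence of 7.2 on DST access and switching is no defect either, because early switch is what the objective names. All of this stands.

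It also stands that protocol section 8 and SAP 1 assign the early-indicator question to the interim analysis, and that the referral comparison is kept in 7.5. With about 2% resistant, referral load is close to the false-positive rate: the proportion referred equals (1 − specificity) + 0.02 × [sensitivity − (1 − specificity)], which is within 2 percentage points of 1 − specificity. The cost side of the algorithm is therefore largely covered, and what is missing is sensitivity, the least precise quantity.

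Three stronger readings are tempting but unsupported:
- A reader might infer that the SAP abandons objective 2. It follows one of two protocol definitions.
- A reader might infer that SAP 2.2 conceals the omission by mentioning only an addition. That sentence concerns objectives; all five are retained and a sixth is added, so it is accurate.
- A reader might infer that specificity, or a separate estimate for high-level mutations, was dropped. Section 8.3.4 plans neither.

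The reply does not explain why an analysis planned in 8.3.4 is absent from the final analysis without comment. Imprecision is a weak reason, since the SAP keeps the 7.2 comparison on the same 10 or so patients per arm.

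**Conclusion.** The point holds as a gap between documents that starts inside the protocol. Sections 3 and 8.3.4 define objective 2 differently. The SAP follows section 3, keeps the referral part of 8.3.4, and leaves the sensitivity of FDA and auramine for initial resistance out of the final analysis without giving a reason. Neither the interim figure nor the ROC curves fill the gap.

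The size is modest. The estimate would rest on about 10 resistant patients, assuming that the protocol's 2010-based expectation holds and that nearly all have a usable baseline sequence and week-2 smears. It would be descriptive, with an interval such as 49% to 94%. No primary efficacy or safety conclusion changes. The value lies in the design of the next study, for which a planned estimate can be had from data already being collected. The unpaired test in SAP 7.5 is a separate, small error that the same edit can correct.

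**What to change.** 1. Reconcile protocol section 3 and 8.3.4 so that objective 2 has one definition, with the stain comparison either placed under it explicitly or moved to objective 5.
2. Add to SAP 7.2, for the final analysis and for all intervention patients with a baseline rpoB result, the sensitivity with Wilson 95% interval of the week-2 FDA criterion and of the same criterion applied to the auramine counts. Label it descriptive. If the sponsor prefers to omit it, state why.
3. Specificity can be reported from the same table, marked as an addition. With about 490 patients without resistance, its half-width is at most about 1.96 × √(0.25/490) = 4.4 percentage points.
4. Compare the two stains, including the referral proportions in SAP 7.5, by a paired method such as McNemar's test in place of the chi-squared or Fisher test. Since management follows FDA only, state that the auramine referral figure is what the criterion would have produced.

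The cost is one extra table with wide intervals, a SAP paragraph and a protocol clarification. No further tests or visits are needed.

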8.3.5 Subgroup analyses

In addition to the main results, pooling new and retreatment cases, all data will be described for new and retreatment TB cases separately.

8.3.6 Multiplicity and Missing Data

As this is a pilot estimation study with a single primary efficacy and safety endpoint, no multiplicity adjustments are needed. An interim analysis will be performed on the end-of treatment data, but this analysis will be done after recruitment is completed and will not influence for continuation of the study. The DSMB will only review safety data and will not stop the study for efficacy advantages.

The handling of missing data will be specified in the SAP. In the intention-to-treat analysis, patients who are lost-to-follow-up will be counted as treatment failures, unless they are known to have moved outside of the area.

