Effective TB control is through detection and treatment of active cases. Treatment requires a combination of drugs and long duration (regimens of at least 6 months). The main first-line drugs are rifampicin and isoniazid, and resistance to both defines MDR-TB which proves impossible to cure with these and other first-line drugs (pyrazinamide, ethambutol, streptomycin). MDR-TB treatment is far more difficult and needs second-line drugs. Among the greater variety of these drugs only a few are sufficiently active, i.e. the later generation fluoroquinolones (mainly gati- and moxifloxacin) and the 2nd-line injectables (2LI). If MDR-TB develops resistance to these two groups as well, an ultra-resistant form develops called XDR-TB; with only one of both groups resistant this is called pre-XDR-TB. MDR-TB treatments are difficult, toxic, expensive and yield highly unsatisfactory results in almost all NTPs. In the DF area, a short and highly effective MDR-TB treatment was developed and has been used with very good results for already 10 years (see further).

The International Union against Tuberculosis and Lung Disease (Union) and the WHO recommend a cascade of TB treatment regimens each aiming at very high but not 100% effectiveness, while allowing a small percentage of failure and relapse cases to start the next regimen in the cascade. The switch to the next higher [sequentially used and “higher” in complexity] regimen is meant to be made as early as possible. In practice this switch is often made too late, since it depends on careful microscopy to identify suspects in need of rapid drug susceptibility testing, and their efficient referral. Particularly patients with MDR-TB may die, default or acquire resistance to more drugs before being recognized as having MDR-TB and put on an appropriate treatment regimen. For some patients with extensive disease and patients with HIV infection, 6 months of the standard primo-treatment (Cat. 1) is too short, leading more frequently to relapse. The current standard first-line

drug retreatment regimen (Cat. 2) is more toxic but not more effective for MDR-TB than the current Cat. 1, and it has only a marginal advantage for other types of drug-resistant TB at the risk of amplification of resistance.

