New cases: Compared to standard regimen dosing of rifampicin is doubled, while standard dose isoniazid, pyrazinamide and ethambutol are maintained, i.e. 2 months of HRhZE followed by 4 months of HRh (6 months)

Retreatment cases: retreatment cases randomized to the intervention arm receive the same care as new cases in the same arm.

Any patients with *MDR TB detected* at any time will be switched to 4 months of KHPtoGCEZ followed by 5 months of GCEZ (MDR regimen)

Testing

In addition to standard monitoring (as described above for the control arm), patients in the intervention arm will have sputum tested by auramine and FDA smear after the first and again after the second week of intensive phase treatment. Management decisions will be made after 2 weeks of intensive phase, based on remaining numbers and decline of AFB on FDA staining, but not based on continuing fever. Those with min. 1 log decline in the number of AFB, or who are already negative, would continue the unaltered regimen. Those not meeting these criteria would be referred for rapid DST by slide DST and/or Xpert MTB/RIF, depending on ease of referral.

This open label, randomised clinical trial is intended as a pilot study on the efficacy and safety of high-dose rifampicin and feasibility and added value of auramine and/or FDA vital staining sputum smear after 2 weeks of intensive treatment phase. If this proof-of-concept study provides substantial indication of benefit without indication of excess toxicity, the data from the study will be used to design a larger scale, cluster-randomized study. The aim of this cluster randomised study would be to provide definite proof of the benefit of the intervention on adverse treatment outcomes and lack of excess toxicity associated with high dose rifampicin. In addition, the cluster-randomized study would provide a more precise assessment of the suppression and prevention of (acquired) resistance endpoints.

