Unknown :	The outcome of the AE is not known because the patient did not return for follow-up (lost to follow-up)

All SAEs will be compiled by the clinic supervisor on the paper report form for the corresponding visit, and completed by the Medical Officer in charge of the hospitalization as appropriate. The Investigator will systematically check and validate the paper records on SAE and other points during his supervision visits to clinics and hospitals, and correct / complete as required before entering the data in the electronic CRF. SAE will be registered as soon as treatment has started and up to its end.

There may be situations when an SAE has occurred and the investigator has minimal information to include in the initial report to the pharmacovigilance. However, it is very important that the investigator always makes an assessment of causality for every event prior to transmission of the report to the pharmacovigilance. The investigator may change his/her opinion of causality in light of follow-up information, amending the SAE-report form accordingly.

All SAE's whether or not deemed drug related or expected must be reported immediately or within 24 hours (one working day) using the SAE Notification Form by telefax or email to:

Clinical Trials Unit
Institute of Tropical Medicine
[name]
[name]
[contact]
Email: [contact]

The title of the e-mail/fax should mention the name of the study code, the patient code and the wording “SAE – Initial/follow up report”.

Line listings of all reported SAE's will be sent at least quarterly to the DSMB, and on a yearly basis to the IRB of the Union, ITM and the EC of UZA. They will also be sent yearly to the study coordinator in Bangladesh to submit these to the respective Authorities and/or ECs.

The Principal Investigator is responsible to report the SAE to the relevant Institutional Ethics Committees and the Bangladesh Regulatory Authorities immediately or according to the deadline established by each Ethics Committee.

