7.2 Data and Safety Monitoring Board

A Data and Safety Monitoring Board (DSMB) with at least 3 independent members will be established for the purpose of providing independent advice on the quality of the data produced and the safety of the treatment tested, so contributing to safeguarding the interests of the trial subjects. Based on the review of the (safety) data, the DSMB can advise the sponsor to modify, halt, discontinue, or continue the trial.

Two types of interim analyses are performed during the trial. The DSMB will meet quarterly after the start of enrolment of the first patients and assess toxicity data to safeguard the study participants safety. The formal interim analysis of the toxicity and efficacy to aid the design of a follow-up study will only be performed when treatment has completed for all patients as full information is needed for the complete treatment period.

A DSMB charter, where the relevant terms of reference including any stopping rules if deemed appropriate are clearly defined, as well as the composition and independency of the Board, will be approved and signed for approval by each member of the DSMB.

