11.4 Confidentiality

All patients' data will be coded in the CRF and database by means of a unique subject assigned patient study number. The documents which can identify the patients, e.g. the ICF's, laboratory print-outs and medical record, will only be accessible to the relevant study staff and to study monitors, auditors and inspectors only under confidentiality agreements.

Patient integrity and safety are safeguarded by on-site monitoring and by an independent data safety monitoring board, which can steer the study as it deems necessary or strongly suggest the sponsor to prematurely terminate the trial if necessary.

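### The DSMB's safety-only remit means bacteriological failures are not compared by arm until every first course has ended; a descriptive, harm-only table would close the gap

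*Protocol*

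**What the plan says.** **Remit.** Protocol 8.3.6 restricts the board: "The DSMB will only review safety data and will not stop the study for efficacy advantages". Section 7.2 is narrower: "The DSMB will meet quarterly after the start of enrolment of the first patients and assess toxicity data". Under 7.1, line listings of reported SAEs "will be sent at least quarterly to the DSMB". Section 11.4, by contrast, describes a board "which can steer the study as it deems necessary". Section 7.2 leaves terms of reference and any stopping rules to a charter that is not among the documents.

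**First comparison by arm.** Section 7.2 says the formal interim analysis of toxicity and efficacy "will only be performed when treatment has completed for all patients as full information is needed for the complete treatment period". Section 8 places it 9 months after the end of recruitment, and 8.3.6 adds that it does not affect continuation.

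**Earlier look.** SAP section 5 describes an analysis after the first 500 patients. It covers referral for rapid DST at 2 weeks and resistance missed, split by new and retreatment cases, and has no effect on conduct.

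**Outcomes.** Protocol 3.1 defines failure as positive sputum at month 5 of treatment or later. Neither failure nor new rifampicin resistance is among the SAE criteria in 7.1.

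**Retreatment cases.** Controls receive Cat. 2 for 8 months, including streptomycin. Under 2.1, "retreatment cases randomized to the intervention arm receive the same care as new cases in the same arm", which means 6 months with double-dose rifampicin and no streptomycin. Section 1.1 says of Cat. 2 that "it has only a marginal advantage for other types of drug-resistant TB at the risk of amplification of resistance".

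**The concern.** Declining to stop for benefit is sound in a pilot of this size. But the same sentence also keeps loss of efficacy from the board, and in tuberculosis an excess of failures is a harm to patients.

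In new cases the intervention keeps the same drugs and duration and doubles rifampicin. In retreatment cases it also drops streptomycin, gives pyrazinamide and ethambutol for less time, and ends two months sooner. Section 8.1 calls the trial a pilot to estimate differences, so a disadvantage in that stratum cannot be ruled out beforehand. If a large one existed, the quarterly meetings would pass without the data that could show it. Rifampicin-susceptible failures in the intervention arm are restarted on the high-dose regimen (5.1), so an unnoticed deficit could also mean repeat exposure.

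**Working it through.** **1. Recruitment time (reproduces the plan).** Inputs from Protocol 4.3: 2000 cases a year, 65% smear-positive, 5% refusal.
2000 × 0.65 × 0.95 / 12 = 102.9 per month; 1000 / 102.9 = 9.7 months. The protocol says 9 to 10.

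**2. Calendar, assuming even accrual.**
- First possible failure: study month 5.
- Last intervention course ends: 9.7 + 6 = month 15.7.
- Last Cat. 2 course ends: 9.7 + 8 = month 17.7.
- First comparison of failures by arm: 9.7 + 9 = month 18.7.
- Gap: 18.7 − 5 = 13.7 months; 13.7 / 3 = 4.6, so four or five quarterly meetings.

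**3. What the board would see in that gap.**
- Deaths and other SAEs: yes.
- Failures declared because at least two drugs were changed for adverse events: possibly, through toxicity review.
- Bacteriological failures, relapses and MDR switches by arm: no.
- The first-500 analysis does not fill the gap. It contains no failures and no acquired resistance.

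**4. Size of the retreatment stratum.** The study's share is not given. The national figure in 1.1 is 7366 / 100,000 = 7.4%; 20% is taken as an assumed upper value. Per arm: 1000 × 0.074 / 2 = 37, up to 1000 × 0.20 / 2 = 100.

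| | Month 9 | Month 12 |
|---|---|---|
| Reached month-5 smear | (9 − 5) / 9.72 = 41%: 15 to 41 per arm | (12 − 5) / 9.72 = 72%: 27 to 72 per arm |
| Intervention cases still on first 6-month course | (9 − 3) / 9.72 = 62%: 23 to 62 | (9.72 − 6) / 9.72 = 38%: 14 to 38 |

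**5. What such a table could show.** Protocol 8.4 gives about 2% failures, new and retreatment pooled. For the full stratum that is 37 × 0.02 = 0.7 to 100 × 0.02 = 2 failures per arm. A split of 0 v 6 is needed for p < 0.05 with Fisher's test at any size from 37 to 100 per arm. Power of a two-sided 5% Fisher test:

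| Failure, control v intervention | Month 9 (15 to 41 per arm) | Month 12 (27 to 72 per arm) |
|---|---|---|
| 2% v 6% | – | 0.003 to 0.09 |
| 5% v 10% | – | 0.01 to 0.12 |
| 5% v 20% | 0.08 to 0.43 | 0.19 to 0.74 |

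All failure rates in this table are assumptions except the 2%, which is the pooled figure applied to this stratum.

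**6. Which harm appears when.** At month 5 both arms are still on treatment, so a shorter total course cannot have caused a month-5 failure; the difference in drugs could. Harm from duration would appear mainly as relapse. The scheduled relapse visit is 12 months after treatment ends, so month 6 + 12 = 18 at the earliest, after the last first intervention course (month 15.7). Before that, only passively reported relapses would be seen.

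**7. Resistance and MDR switches.** Referral for rapid DST at 2 weeks depends on FDA decline in the intervention arm and on fever in the control arm (2.1). More switches in the intervention arm may therefore be the earlier detection that the design intends. Confirming acquired resistance needs the pre-treatment sequence and spoligotyping in Antwerp (5.4), and isolates go there only periodically. Patients switched before an outcome applies leave the outcome analysis (Protocol 3.1, SAP 4.2), and the acquired-resistance analysis counts only failures and relapses (SAP 7.4). Resistance that arises early thus enters neither comparison, which is a reason to list it.

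**The case against.** The strongest case against is that this safeguard would be weak. The failure rate in the documents leads to about two expected failures per arm at most, and a threefold excess would almost always go unseen. The 5% v 20% scenario has no support in the documents. The relapses that a shorter course might cause come too late for a quarterly table to protect anyone on a first course. By month 12 recruitment has closed and only 14 to 38 intervention retreatment cases remain on treatment. All of this stands, and it limits the claim to a descriptive listing.

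It is also true that individual failures are referred for rapid DST and managed on the result, that deaths reach the board as SAEs, and that retreatment cases found rifampicin-resistant before treatment are not enrolled. The point concerns the comparison between arms, not individual care.

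The charter may give wider terms. It has not been seen, but if it does, it conflicts with the restriction in 8.3.6, and the wording would still need to be reconciled.

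A reader might infer from 1.1 that the protocol expects the intervention to be worse than Cat. 2 in retreatment cases. It does not: the same sentence calls Cat. 2 more toxic and no more effective for MDR-TB. The remark shows only that a disadvantage in other drug-resistant disease is conceivable.

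**Conclusion.** The point holds as a gap in monitoring. As written, the only independent body does not see bacteriological failures by arm for about 13.7 months after they can first occur, until all first randomised courses have finished. The calendar rests on the protocol's own recruitment figures and even accrual; the retreatment numbers rest on an assumed share of 7.4% to 20%.

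Three stronger readings are tempting but not supported:
- *That 62% (month 9) or 38% (month 12) of intervention patients would be exposed to the suspected harm.* Those shares apply to the whole arm. The harm in question concerns retreatment cases, a small part of it.
- *That the board could reliably detect inferiority if shown the data.* Only a large excess would be visible.
- *That nobody remains on randomised treatment at the first look.* This is true of first courses; an intervention patient who fails and restarts the high-dose regimen could still be on a second course.

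The change is worth making because it is cheap and serves patient safety, not because harm has been shown.

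**What to change.** Replace the sentence in Protocol 8.3.6, and align 7.2 and the DSMB charter, with wording such as:

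*At each quarterly meeting the DSMB also reviews, in closed session by arm and by new/retreatment stratum, deaths, failures and relapses to date, for harm only. Rifampicin resistance detected after start of treatment and MDR switches are listed separately by time of detection (2-week screen versus later) and by pre-treatment DST or sequencing result where available, because the arms have different 2-week DST triggers. There is no stopping for efficacy advantage.*

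The table should be labelled descriptive. No alpha adjustment is needed, because no look can lead to a claim of benefit.

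Cost: one extra closed table per quarter, plus protocol and charter wording. Deaths, smear outcomes, rapid DST results and switches are already recorded; sequencing results will be incomplete at any given meeting. The downside is that a chance imbalance, or a difference in detection between the arms, may prompt a query from the board.
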